STUDY PROTOCOL: SIT LESS OR EXERCISE MORE: IMPACT ON CARDIOMETABOLIC HEALTH IN MULTIPLE SCLEROSIS.

1. Background

To date, it is clear that sedentary behavior is strongly related to an increased risk of type II diabetes, cardiovascular disease and premature mortality¹. People suffering from chronic disabilities appear to be particularly susceptible to a sedentary lifestyle and inactivity due to primary disease symptoms². To date, this is an important new research topic in Multiple Sclerosis (MS, ~2.3 million people worldwide³, ~10-12.000 diagnosed in Belgium⁵⁻⁷)⁸ treatment. MS is a progressive, autoimmune, neurodegenerative disorder of the central nervous system (CNS) that predominantly affects young to middle-aged adults. It is characterized by a chronic inflammatory process that causes demyelination and axonal damage across the CNS⁹. Clinical manifestations include spasticity, tremor, paralysis, walking difficulties and cognitive abnormalities¹⁰.

Persons with MS (PwMS) have a 40% lower daily step count compared to healthy inactive persons¹¹ and tend to accumulate their sedentary time in longer bouts¹². As described above and similar to other chronic conditions, a sedentary lifestyle also makes PwMS more vulnerable to the accumulation of important cardiometabolic comorbidities that seem inactivity-related rather than a direct result of non-reversible tissue injury¹³. Such comorbidities include impaired whole body glycaemic control, an abnormal blood lipid profile, an unhealthy body composition and hypertension^{14, 15}. In this respect, it is important to note that corticosteroids, which are often used to treat MS patients pharmacologically¹⁶, elevate fasting glucose and insulin concentrations and induce insulin resistance in healthy controls (HC)¹⁷ therefore probably also increase several cardiometabolic risk factors in MS.

An important first line treatment strategy to improve such cardiometabolic comorbidities involves exercise therapy and a more active lifestyle. So far however, more physical activity usually refers to moderate- to vigorous physical activity (MVPA), as evidenced in current activity guidelines. Here, adults aged 18 to 65 years are recommended to perform at least 30min of moderate-intensity aerobic physical activity on five days of the week or vigorous-intensity physical activity for a minimum of 20min on three days of the week¹⁸. These guidelines however do not describe the activity level of the remaining 1410min per day. In this respect, evidence is growing that sedentary time, independent of the (dis)practice of MVPA, is an important independent health risk factor^{19, 20}. In MS, MVPA is a well-studied topic and frequently applied complementary treatment strategy leading to a wide range of important functional improvements in different areas of cardiorespiratory fitness, muscle strength, balance, fatigue, cognition, quality of life and respiratory function²¹. In this population effects on cardiometabolic risk markers however are less prominent and contradictory²². Consequently, any strategy that also improves cardiometabolic health may help to further optimize rehabilitation in MS. Breaking up and reducing sedentary time with easy, daily activities such as household activities and other activities which increase light-intensity walking and standing, known as non-exercise physical activity (NEPA) may be such a strategy.

NEPA has already been shown to significantly improve cardiometabolic risk markers in healthy, sedentary subjects²³, type II diabetes patients²⁴ and obese adults²⁵ and it involves lower intensity physical activities that are probably more feasible than MVPA for PwMS. Moreover, with comparable activity workloads, reducing sitting time by NEPA of longer duration decreases insulin levels and fasting lipid levels more than performing one MVPA bout^{23, 24} that is usually described in current activity guidelines¹⁸. So far however, acute MVPA and NEPA effects on cardiometabolic health in this population have never been described. Therefore, the aim of this study is to investigate whether (1) cardiometabolic health (glycaemic control, blood lipids, inflammation markers and blood pressure) of persons with MS improves when sedentary time is reduced and (2) NEPA results in better cardiometabolic health parameters than (a shorter daily bout of) moderate-intensity exercise when workload of both activities is identical in this population.

2. Methods

A flowchart of the study design is provided in Figure 1. The design of the study, the different activity regimes and the continuous activity monitoring are based on previous research in sedentary subjects²³ and type II diabetes patients²⁴. For practical reasons (subjects are aware of their activity regimen), it is not possible to blind the study. The study is an intervention study with a cross-over design. Participants will follow four regimes of 4 days each including a control, a sit less, a sit and an exercise regime. The order of the sit and sit less regimes will be randomized. Each activity regime will be followed by a wash-out period of 10 days during which subjects will continue their normal lifestyle. Fasting glucose, insulin, inflammation parameters, lipids and blood pressure will be determined at the end of each regime (on day 5).

[figure not shown]

Fig. 1: Flowchart study design. The order of the sit less and sit regime will be randomised. Between each activity regime a wash-out period of 10 days takes place. Abbreviations: d: days, v: visit (v-1,-2: screening visits, v1,3,5,7: attachment of ActivPAL – v2,4,6,12: test days + removing of ActivPAL – v8,9,10,11: exercise sessions)

2.1 Visits

An overview of study visits is provided in Table 1, they include screening visits before start of the study, activPAL (activity monitor) installation/attachments before the start of each activity regimen, training sessions during the training regime and test days and removal of the ActivPAL following each intervention period. The visit structure is described in Table 2.

Week	Monday	Tuesday	Wednesday	Thursday	Friday	Saturday	Sunday
1					v1: activPAL	Control regime	Control regime
2	Control regime	Control regime	v2: blood samples				
3					v3: activPAL	Sit less/sit regime	Sit less/sit regime
4	Sit less/sit regime	Sit less/sit regime	v4: blood samples				
5					v5: activPAL	Sit/sit less regime	Sit/sit less regime
6	Sit/sit less regime	Sit/sit less regime	v6: blood samples				
7					v7: activPAL	v8: training session 1	v9: training session 2
8	v10: training session 3	v11: training session 4	v12: blood samples				

Table 2: specific visit information		
Info session	Day -...	Informed consent
Screening	Visit -2 Visit -1	- Resting ECG - Graded exercise test + explanation polar M200
Visit 1	Day 0	End of wash-out period (= day before the start of the control regime; day 1) - attachment of ActivPAL
Visit 2	Day 5	Start of wash-out period (= day after the end of the control regime) - Blood sampling + OGTT + blood pressure - Removing ActivPAL
Visit 3	Day 14	Last day of wash-out period (= day before the start of the sit less/sit regime) - Attachment of ActivPAL + instructions for activity pattern
Visit 4	Day 19	Start of wash-out period - Blood sampling + OGTT + blood pressure - Removing ActivPAL
Visit 5	Day 28	Last day of wash-out period (= day before the start of the sit/sit less regime) - Attachment of ActivPAL + instructions for activity pattern
Visit 6	Day 33	Start of wash-out period - Blood sampling + OGTT + blood pressure - Removing ActivPAL + feedback on accelerometer data
Visit 7	Day 42	Last day of wash-out period (= day before the start of the exercise regime) - Attachment of ActivPAL + instructions for activity pattern
Visit 8	Day 43	Start of exercise regime - Cycling
Visit 9	Day 44	Day 2 of exercise regime - Cycling + feedback on accelerometer data
Visit 10	Day 45	Cycling
Visit 11	Day 46	Day 4 of exercise regime - Cycling + feedback on accelerometer data
Visit 12	Day 47	Day after the end of the exercise regime - Blood sampling + OGTT + blood pressure - Removing ActivPAL

2.2 Subjects

Sample size

The study population will involve 31 PwMS. The number of subjects needed for this study has been calculated based on triglyceride level changes in a comparable study by Duvivier and colleagues²⁴ with 3 activity regimes (paired t-test: effect size 0.71, correlation 0.50, 2-sided α of 0.05/6, power 80%, drop-out 10%). Serum triglycerides, which are significantly elevated in PwMS¹⁵, are an important cardiometabolic risk marker²⁶ and improve consistently in 2 comparable studies in sedentary subjects and type II diabetes patients^{23, 24}.

Recruitment

PwMS will be recruited using online and paper advertisements (local physiotherapists, MS-Liga, hospitals). All subjects will be informed in detail and will be asked to provide written informed consent. The study will be approved by the medical ethical committee of Hasselt University and will be performed at Hasselt University (Diepenbeek, Belgium) between February 2019 and September 2020 in accordance with the principles of the Declaration of Helsinki. The present study is registered at clinicaltrials.gov.

Screening

The following subject characteristics will be assessed: age, sex, medications, smoking history and family history of coronary artery disease, type of MS (relapsing remitting, secondary progressive, primary progressive), duration of MS and Expanded disability status scale (EDSS) score.

In order to be eligible to participate in this study, a subject must meet all of the following criteria:

- Signed informed consent
- Men and women ≥ 18 years old
- Clinical diagnosis of MS (McDonald criteria)
- EDSS ≤ 5
- Daily internet access

A potential subject who meets any of the following criteria will be excluded from participation in this study:

- Reported participation in another biomedical trial which may have an effect on blood parameters one month before the pre-study examination or during the study
- Blood donation in the past three months
- Pregnancy or intention of becoming pregnant
- Reported dietary habits: medically prescribed diet, slimming diet
- Reported weight loss ($>2\text{kg}$) in the last three months prior to the screening
- Alcohol use > 20 units per week (during the last 3 months)
- Experimental drug use (during the last 3 months)
- Medication changes (during the last month)
- Medical conditions which make participation in the study not responsible:
 - Heart failure NYHA 3 or higher
 - Angina pectoris or signs of cardiac ischemia during exercise testing
 - Mental or physical disability
- Based on historical information not able to walk for 3h per day and stand for 4h per day (e.g. intermittent claudication)

There will be two screening visits, organized at least 10 days before start of the study (Saturday of week 1, see table 1). During the first screening visit, a resting electrocardiogram (ECG) will be assessed, which will be evaluated by a trained professional for medical safety of maximal exercise testing (until volitional exhaustion in combination with a respiratory exchange ratio ≥ 1.1 or failure to maintain 45 RPM). This will be done with an incremental exercise test on a bicycle ergometer during the second screening visit, to assess maximal workload capacity (W_{\max}). The W_{\max} is necessary to calculate intensity of training sessions in the exercise regime (see 3.6 exercise intensity). Subsequently, participants will receive a Polar M200 activity tracker and explanation about its use (see 3.5 activity tracking).

2.3. Randomization

At the end of visit -1 subjects will be randomised, if no contra-indications have been observed during the screening. The two below-mentioned schemes (Fig. 2) will be taken into randomisation 15 times. For the last subject the scheme will be chosen randomly

[figure not shown]

Fig. 2: allocation to activity regime schemes.

The randomisation will be done by a member of the research team by drawing a sealed, non-translucent envelop with herein written the scheme. After randomisation, the first activity regime will start within ± 10 days. The regimes will always start on the same day (Saturday) to minimize bias.

2.4 Regimes

During each activity regime (4 days), participants will be asked to spend 8h sleeping/lying. Subjects will be allowed to sleep \pm 2 hours less or more and replace this sleeping time by sitting (more or less) as long as sleeping time is the same during all regimes. Each activity regime is followed by a wash-out period of 10 days during which subjects can continue their normal lifestyle, but are not allowed to perform more than 60min of MVPA.

Control regime

To provide feedback on how to change activity patterns in order to comply with the subsequent activity regimes, subjects will start with the control regime. This is a baseline measurement of physical activity during which subjects will be instructed not to change activity patterns during these four days and to note all activities they perform.

Sit regime

Here, participants spend 14h of their day sitting, 1h walking and 1h standing. According to the compendium of Ainsworth et al. (2011)²⁷, this corresponds with a daily workload of activities (DWA) of 27 metabolic equivalents (MET's) per day.

Sit less regime

Each day will consist of 3h walking, 4h standing and 9h sitting. These time frames are chosen to result in a comparable DWA increase as the exercise regime compared to the sit regime (+7 MET's)²⁷. The additional 2h of walking and 3h of standing, compared to the sitting regime, will be done in a minimum of four bouts with a time interval of > 1h. The subjects will be instructed to walk on a slow pace. i.e. 2-3 km/h (e.g. walking during shopping and work related walking in an office).

Exercise regime

One hour of sitting in the sit regime will be replaced with 1 training session (1h) on a cycle ergometer in the research center. The remaining hours of each day have to be spent as follows: 13h sitting, 1h walking and 1h standing for daily care. The intensity of the training session (50-60% of W_{max}) results in a DWA of 34.5 MET's according to the compendium of physical activities²⁷. Duration of training sessions will be adapted individually with ActivPAL data of the sit less and sit regime to identically match DWA increase between the sit less and exercise regime, compared to the sitting regime. Details can be found in '3.6 exercise intensity'.

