2.6. Exercise intensity

To ensure that DWA will be the same during the sit less and exercise regime, ActivPAL data of the sit less and sit regime will be used to individualize training sessions during the exercise regime. ActivPAL is able to estimate workload of activities in MET's. One MET is the energy expenditure of an individual in resting condition ($3.5 \text{ mL} \cdot \text{kg}^{-1} \cdot \text{min}^{-1}$). The amount of MET's as provided by the activPAL is based on how many steps are taken, acceleration and amount of hours walking, standing and sitting/lying. The ActivPAL will be taken off during cycling in the exercise regime. The measurement error of the activPAL in estimating this energy expenditure has been reported to be low for sedentary and light-intensity activities but high for moderate- and vigorous-intensity activities²⁹.

It will be calculated how long subjects need to cycle at an intensity of 50-60% W_{max} to match the workload of the training session with the DWA increase of the sit less regime, compared to the sit regime. The workload of cycling at 50-60% of W_{max} will be calculated using the following equation²⁴: $\text{MET} = 0.0545 \cdot \text{Watt} + 1.4561$ ($R^2 = 0.946$), which describes the relationship between MET's and Watts, based on literature included in the compendium of physical activities²⁷ that actually measured energy expenditure over a range of workloads. The DWA in the sit less and sit regime will be measured with the ActivPAL as described above.

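### The stated 34.5 MET exercise day does not follow from 50-60% Wmax, and its fixed hours and matching rule conflict with the individually calculated session

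*Combined protocol and SAP*

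**What the plan says.** Section 2.4 sets lying time for every regime: "participants will be asked to spend 8h sleeping/lying". In the sit regime "participants spend 14h of their day sitting, 1h walking and 1h standing", and "this corresponds with a daily workload of activities (DWA) of 27 metabolic equivalents (MET's) per day". For sit less, "Each day will consist of 3h walking, 4h standing and 9h sitting", chosen to add 7 MET's to the sit day.

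The exercise regime replaces one hour of sitting with a one-hour cycling session. For the rest of the day: "The remaining hours of each day have to be spent as follows: 13h sitting, 1h walking and 1h standing for daily care". The session intensity, 50-60% of Wmax, "results in a DWA of 34.5 MET's according to the compendium of physical activities". The next sentence makes the session individual: "Duration of training sessions will be adapted individually with ActivPAL data of the sit less and sit regime", so that the increase over the sit day is identical to that of sit less.

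Section 2.6 (cited in 2.4 as 3.6) gives the method: "It will be calculated how long subjects need to cycle at an intensity of 50-60"% of Wmax, so that the workload of the session equals the increase measured by activPAL. The session workload comes from MET = 0.0545 × Watt + 1.4561.

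The daily totals are sums of hours times MET, written below as MET-h.

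**The concern.** A percentage of Wmax fixes relative effort and not energy expenditure, so one percentage band cannot give one daily total for all subjects. Three further items do not fit together: an increase of 7.5 beside one of 7, a list of hours that fits only a 60-minute session beside an individual duration, and a session that replaces sitting beside a formula that does not deduct the sitting replaced.

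Aim 2 (end of section 1) compares sit less with exercise at identical workload. If the increases differ, the contrast mixes type of activity with amount. If the benefit rises with workload, a shortfall on the exercise day favours sit less, which is the direction the background section expects.

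**Working it through.** **Inputs from the documents.** Sit day 27 MET-h; sit-less increase 7; exercise day 34.5; the hours per regime; 8 h lying; the MET equation; intensity 50-60% of Wmax. **Assumption.** Lying and sitting at 1 MET; the documents state no value for either.

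**1. The plan's own totals.** Let D be the MET for standing and W for walking.
- Sit day: 8×1 + 14×1 + W + D = 27, so W + D = 5.
- Sit less replaces 5 h of sitting with 2 h walking and 3 h standing: 2W + 3D − 5×1 = 7, so 2W + 3D = 12.
- Solution: D = 2, W = 3. The sit-less day is 8 + 9 + 9 + 8 = 34.

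These are plausible values, so sitting at about 1 MET fits the plan. With sitting at 1.3 and lying at 1, W + D = 0.8 and 2W + 3D = 13.5, so W = −11.1, which is impossible. The 34.5 cannot be reproduced, because neither the session MET nor Wmax is given.

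**2. What 34.5 requires.** The exercise day without the session is 8 + 13 + 3 + 2 = 26. One hour must supply 34.5 − 26 = 8.5 MET.
- Watt = (8.5 − 1.4561)/0.0545 = 129.2 W.
- Wmax = 129.2/0.6 = 215 W, or 129.2/0.5 = 258 W.
- Implied increase: 34.5 − 27 = 7.5, against 7 for sit less.

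**3. When a matched session exceeds 60 minutes.** Net of the sitting replaced, one hour suffices if MET − 1 equals the target; gross, if MET equals the target.

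| Target increase (MET-h) | Wmax threshold, net (60%-50%) | Wmax threshold, gross (60%-50%) |
|---|---|---|
| 7 (nominal) | 200-240 W | 170-203 W |
| 5 | 139-167 W | 108-130 W |
| 4 | 108-130 W | 78-93 W |

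Below the threshold the session is longer than one hour. For the first row: (8 − 1.4561)/0.0545 = 120.1 W net and (7 − 1.4561)/0.0545 = 101.7 W gross, each divided by 0.6 and 0.5. The targets of 5 and 4 are assumed, to show the effect of a smaller activPAL-measured increase.

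**4. The day's hours.** 8 + 13 + 1 + 1 = 23 h, which leaves 1 h. The allowance of ±2 h of sleep does not help: it trades against sitting and must be the same in all regimes.

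**5. Net against gross matching.** At 55% of Wmax and a target of 7: net minutes = 60×7/(MET − 1); gross minutes = 60×7/MET; increase after gross matching = 7×(MET − 1)/MET. The Wmax values are assumed.

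| Wmax | MET | Net min | Gross min | Increase if gross | Shortfall |
|---|---|---|---|---|---|
| 80 W | 3.85 | 147 | 109 | 5.18 | 26% |
| 100 W | 4.45 | 122 | 94 | 5.43 | 22% |
| 150 W | 5.95 | 85 | 71 | 5.82 | 17% |
| 200 W | 7.45 | 65 | 56 | 6.06 | 13% |

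The relative shortfall is 1/MET. It does not depend on the target, so it remains if the measured increase is smaller than 7.

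**The case against.** The strongest reply is that 1 h, 13 h and 34.5 are nominal. The 34.5 is credited to the compendium and not to the equation, and that source is not before us. The sentence after it makes duration individual, section 2.6 gives the calculation, and the increases of 7 and 7.5 are only nominal before that calculation. Since 13 h is 14 h minus the nominal hour, a longer session would naturally displace more sitting.

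Much of this stands. The hour is better read as nominal than as a cap, so the documents do not support the inference that subjects will be held to one hour and under-dosed. A reader might also infer that matched sessions will usually exceed an hour. That needs a Wmax distribution and the measured sit-less increase, and the documents give neither. Nor is 215-258 W the threshold for a session longer than one hour: it is the Wmax at which one hour gives 34.5. That any shortfall falls mainly on more disabled subjects is likewise unsupported, because nothing in the documents links Wmax to EDSS.

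The reply does not settle three things. None of the figures is labelled nominal, and the hours are worded as obligatory. Nothing says which hours change when the session is not 60 minutes. The calculation in section 2.6, read literally, does not deliver the identical increase that section 2.4 requires.

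**Conclusion.** The point holds, with modest severity. That 50-60% of Wmax does not determine 34.5 follows from the plan's own equation; the range of 215-258 W rests on sitting at about 1 MET, which the plan's totals support. The conflict between the fixed hours and the individual duration needs no assumption about fitness: any session other than 60 minutes, longer or shorter, breaks the list.

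The part that bears on inference is the matching rule. Gross matching leaves the exercise-day increase short by about 17-22% at an assumed Wmax of 100-150 W (13-26% over 80-200 W), at 55% intensity. Whether the trial would match gross or net cannot be told from the text, so this is the size of an ambiguity and not of a demonstrated error in conduct.

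**What to change.** The sponsor should reconcile the one-hour session, the 13 h of sitting, the 34.5 and the increase of 7 in section 2.4 with the individual calculation in section 2.6. Specifically:

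- Label the nominal figures as such, with the Wmax and MET values they assume, and resolve 7 against 7.5.
- State how the 24 hours are accounted for when the calculated duration is not one hour.
- Write the matching formula explicitly and make it consistent with the identical increase that aim 2 requires, that is, net of the activity replaced.
- Report delivered against calculated workload for each subject. The activPAL is off during cycling, so the session part must come from recorded watts and minutes.

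The inputs are already collected before the exercise regime: Wmax at visit -1 and activPAL data for both sitting regimes by visit 6. The cost is protocol wording and one formula, with no added visits or subjects. The downside is that the exercise-day figure becomes subject-specific. No session length or daily schedule is proposed here; those remain for the sponsor.
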